7.1.5.2.2 Second Course Phase (Retreatment Period for Post-complete Remission Relapse ONLY)

Subjects may be eligible to receive up to an additional 17 cycles (approximately 1 year) of pembrolizumab in the Retreatment Period of this study if the study remains open and the subject meets all of the following conditions:

- Stopped (or completed) initial treatment with pembrolizumab after attaining an confirmed CR by investigator assessment according to respective response criteria
- Was treated for at least 24 weeks (8 cycles) with pembrolizumab before discontinuing therapy
- Received at least two treatments with pembrolizumab beyond the date when the initial CR was declared
- Experienced an investigator-determined confirmed disease progression after stopping their initial treatment with pembrolizumab
- Did not receive any anti-cancer treatment since the last dose of pembrolizumab
- Have a performance status of 0 or 1 on the ECOG Performance Scale
- Demonstrate adequate organ function as detailed in Section 5.1.2
- Female subject of childbearing potential should have a negative urine or serum pregnancy test within 72 hours prior to receiving retreatment with study medication.
- Female subjects of childbearing potential should be willing to use 2 methods of birth control or be surgically sterile, or abstain from heterosexual activity for the course of the study through 120 days after the last dose of study medication (Reference Section

5.7.2). Subjects of child bearing potential are those who have not been surgically sterilized or have not been free from menses for > 1 year.

Note: Abstinence is acceptable if this is the usual lifestyle and preferred contraception for the subject.

- Male subjects should agree to use an adequate method of contraception starting with the first dose of study therapy through 120 days after the last dose of study therapy.

Note: Abstinence is acceptable if this is the usual lifestyle and preferred contraception for the subject.

- Does not have a history or current evidence of any condition, therapy, or laboratory abnormality that might interfere with the subject's participation for the full duration of the trial or is not in the best interest of the subject to participate, in the opinion of the treating investigator.

Subjects who achieved CR and received up to 35 doses (approximately 2 years) of treatment with pembrolizumab may be eligible for up to 17 doses (approximately 1 year) of retreatment. Subjects who restart treatment will be retreated at the same dose frequency as when they last received pembrolizumab.

Confirm subjects are eligible for retreatment as described above. The Second Course Eligibility Visit may be conducted on the day of the first dose, but eligibility must be confirmed prior to dosing. See Section 6.2 – Second Course Trial Flow Chart.

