Hemoglobin ^b	$\geq 8 \text{ g/dL}$
Renal	
Creatinine OR Measured or calculated ^a creatinine clearance (GFR can also be used in place of creatinine or CrCl)	$\leq 1.5 \times \text{upper limit of normal (ULN)}$ OR $\geq 60 \text{ mL/min}$ for subject with creatinine levels $> 1.5 \times$ institutional ULN
Hepatic	
Total bilirubin	$\leq 1.5 \times \text{ULN}$ OR Direct bilirubin $\leq \text{ULN}$ for subjects with total bilirubin levels $> 1.5 \times \text{ULN}$
AST (SGOT) and ALT (SGPT)	$\leq 2.5 \times \text{ULN}$ OR $\leq 5 \times \text{ULN}$ for subjects with liver metastases
Coagulation	
International Normalized Ratio (INR) or Prothrombin Time (PT) Activated Partial Thromboplastin Time (aPTT)	$\leq 1.5 \times \text{ULN}$ unless subject is receiving anticoagulant therapy as long as PT or PTT is within therapeutic range of intended use of anticoagulants $\leq 1.5 \times \text{ULN}$ unless subject is receiving anticoagulant therapy as long as PT or PTT is within therapeutic range of intended use of anticoagulants

^a Creatinine clearance should be calculated per institutional standard.

^b Hemoglobin and platelet requirements cannot be met by use of recent transfusion or growth factor support (G-CSF or erythropoietin) within 2 weeks prior to treatment initiation unless bone marrow infiltration by disease is documented, in which case red blood cell transfusion is allowed.

8. Female subject of childbearing potential should have a negative urine or serum pregnancy within 72 hours prior to receiving the first dose of study medication. If the urine test is positive or cannot be confirmed as negative, a serum pregnancy test will be required.
9. Female subjects of childbearing potential (Section 5.7.2) must be willing to use an adequate method of birth control as outlined in Section 5.7.2 – Contraception, for the course of the study through 120 days after the last dose of study medication.

Note: Abstinence is acceptable if this is the usual lifestyle and preferred contraception for the subject.

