5.7.2 Contraception

Pembrolizumab may have adverse effects on a fetus in utero. Furthermore, it is not known if pembrolizumab has transient adverse effects on the composition of sperm. Therefore, non-pregnant, non-breastfeeding women may only be enrolled if they are willing to follow the Clinical Trial Facilitation Group (CTFG) Guidance (Final Version 2014-09-15, Sections 4.1 and 4.2) for highly effective birth control as outlined below, or are considered to be highly unlikely to conceive. Highly unlikely to conceive is defined as:

1. surgically sterilized, or
2. postmenopausal (defined as at least 12 months with no menses without an alternative medical cause; in women <45 years of age a high follicle-stimulating hormone [FSH] level in the postmenopausal range may be used to confirm a post-menopausal state in women not using hormonal contraception or hormonal replacement therapy. In the absence of 12 months of amenorrhea, a single FSH measurement is insufficient), or
3. not heterosexually active for the duration of the study. Subjects should use birth control methods that can achieve a failure rate of less than 1% per year when used consistently and correctly and are considered as highly effective birth control methods.

Such methods include:

- Combined (estrogen and progestogen containing) hormonal contraception associated with inhibition of ovulation:
 - Oral
 - Intravaginal
 - Transdermal
- Progestogen-only hormonal contraception associated with inhibition of ovulation:
 - Oral
 - Injectable
 - Implantable
- IUD
- Intrauterine hormone-releasing system (IUS)
- Bilateral tubal occlusion
- Vasectomized partner
- Sexual abstinence

Subjects should be informed that taking the trial medication may involve unknown risks to the fetus (unborn baby) if pregnancy were to occur during the trial. In order to participate in the trial, subjects of childbearing or reproductive potential must adhere to the contraception requirement (described above) from the day of trial medication initiation (or 14 days prior to the initiation of trial medication for oral contraception) throughout the trial period up to 120 days after the last dose of trial medication. If there is any question that a subject of childbearing or reproductive potential will not reliably comply with the requirements for contraception, that subject should not be entered into the trial.

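### The retreatment contraception item in Section 7.1.5.2.2 does not match inclusion 9 or the Section 5.7.2 it cites, either on the number of methods or on who needs contraception

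*Combined protocol and SAP*

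**What the plan says.** Section 7.1.5.2.2 of the protocol lets a subject who relapses after a complete response receive a second course if "the study remains open and the subject meets all of the following conditions". Three statements in that list matter here.

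- Contraception: "Female subjects of childbearing potential should be willing to use 2 methods of birth control or be surgically sterile", or abstain, through 120 days after the last dose. The item refers the reader to Section 5.7.2.
- Definition: "Subjects of child bearing potential are those who have not been surgically sterilized or have not been free from menses for > 1 year".
- Pregnancy test: "Female subject of childbearing potential should have a negative urine or serum pregnancy test within 72 hours prior to receiving retreatment".

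At first entry, inclusion 9 in Section 5.1.2 says that women of childbearing potential "must be willing to use an adequate method of birth control as outlined in Section 5.7.2". Section 5.7.2 sets the standard: "Subjects should use birth control methods that can achieve a failure rate of less than 1% per year when used consistently and correctly". It then lists acceptable methods, among them hormonal contraception, an intrauterine device, a hormone-releasing intrauterine system, tubal occlusion and a vasectomized partner. It treats three groups as highly unlikely to conceive: surgically sterilized women, women who are "postmenopausal (defined as at least 12 months with no menses without an alternative medical cause", and women who are not heterosexually active. Its requirement runs for the whole trial period and 120 days beyond the last dose, so it also covers a second course.

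**The concern.** Both rules bear on the same woman at the same visit. Sections 2.1 and 5.8.1 tie retreatment to the safety parameters of the entry criteria. Flow chart 6.2 note e, and the end of Section 7.1.5.2.2, require the retreatment list to be confirmed before dosing. A site therefore has two answers to two practical questions: how many methods are needed, and which women need one.

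The first mismatch could delay or deny retreatment to a relapsed patient whose contraception the protocol otherwise accepts. The second, on the apparent intent of the sentence, could lead a site to treat a woman as not needing contraception when Section 5.7.2 says she does. That section warns of possible harm to a fetus. Drug and dose are the same in both courses, and no reason for a different rule is given.

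**Working it through.** The plan states no figure on this point, so the check is first a comparison of texts and then a rough count of the women affected.

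**Comparison**

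| Question | Inclusion 9 and 5.7.2 | 7.1.5.2.2 |
|---|---|---|
| Methods needed | One; inclusion 9 uses the singular, and 5.7.2 lists stand-alone options without asking for a combination | Willingness to use two |
| Exempt for lack of menses | At least 12 months, with no other medical cause | More than 1 year, cause not mentioned |
| Duration | To 120 days after the last dose | Same |

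**Case 1, number of methods.** A woman uses a hormone-releasing intrauterine system and does not want a second method. Under inclusion 9 and 5.7.2 she qualifies. Under 7.1.5.2.2 she fails a condition in a list where all must hold. The list also has an investigator-opinion item, but that can only exclude a subject; it cannot waive another item.

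**Case 2, who needs contraception.** The definition joins two negatives with *or*, so it can be read in two ways.

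- As apparently intended, a woman is exempt if she is sterilized or has had no menses for over a year. By the cohort definitions, every subject had salvage chemotherapy or an autologous transplant before entry, so amenorrhoea caused by treatment is plausible. Such a woman, if heterosexually active, is not postmenopausal under 5.7.2. In 7.1.5.2.2 she falls outside both the contraception item and the pregnancy-test item.
- Read literally, she must be both sterilized and free of menses to be exempt. An unsterilized postmenopausal woman is then of childbearing potential, although 5.7.2 exempts her.

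Neither reading agrees with 5.7.2.

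**Count.** Section 4.3 gives a CR rate of 22.4% among 210 treated, by central review: 0.224 × 210 = 47. The stated interval of 16.9% to 28.6% corresponds to about 36 to 60 subjects. The documents give no sex split, menopausal status or retreatment count, so the following are assumptions: 40–60% women; 50–90% of them of childbearing potential under 5.7.2; 5–40% of CR subjects coming to retreatment.

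Retreatment candidates of childbearing potential = 47 × women × childbearing potential × retreated:

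- low: 47 × 0.40 × 0.50 × 0.05 = 0.5
- middle: 47 × 0.50 × 0.70 × 0.20 = 3.3
- high: 47 × 0.60 × 0.90 × 0.40 = 10.2

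Of these, assume 10%, 20% or 30% have more than a year of treatment-related amenorrhoea:

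- low: 0.5 × 0.10 = 0.05
- middle: 3.3 × 0.20 = 0.7
- high: 10.2 × 0.30 = 3.0

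The first set of figures is a ceiling for Case 1. It includes women who would accept a second method or who abstain. On the intended reading it also includes the women in the second set, who would not be asked for two methods.

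**The case against.** A reader might infer that the two rules contradict each other outright. They do not. A woman who uses two methods, at least one from the 5.7.2 list, satisfies inclusion 9, 5.7.2 and the retreatment list together. The item also tests willingness, not current practice, so using one method now does not by itself disqualify her; declining a second one does. An extra condition at re-entry is stricter, and strictness alone is no error. What remains is that the item cites 5.7.2 for a requirement that 5.7.2 does not contain.

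A reader might also infer that the protocol permits re-dosing a fertile woman with no contraception and no pregnancy test. The documents do not support that either. The exemption arises only on one reading of an ambiguous sentence. Even then, 5.7.2 still applies throughout the trial, the entry safety parameters apply at retreatment, and exclusion 12 bars subjects who are pregnant or expecting to conceive. Flow chart 6.2 note n separately calls for a pregnancy test at Cycle 1 in women of reproductive potential. To re-dose such a woman without contraception, the site would have to overlook 5.7.2. The cover is partial because note n does not define its term and the protocol does not say which text prevails.

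The FSH clause in 5.7.2 narrows the group further. It lets a postmenopausal-range value support menopausal status in women under 45 not using hormones, and how the section treats permanent ovarian failure after chemotherapy is not spelled out.

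Nor can one say with confidence that the wording was not a deliberate tightening. That argument needs the list to be stricter on one point and looser on the other, which holds only on the intended reading. Finally, the current amendment concerns an extension study after this trial ends, so few retreatment decisions may remain.

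**Conclusion.** The mismatch is real and sits in an operative eligibility rule, but it is minor. On the number of methods it is an eligibility inconsistency, not a safety gap. On the definition, 7.1.5.2.2 departs from 5.7.2 on either reading, and only the apparent intended reading touches safety, with partial protection elsewhere.

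About 3 women (0.5 to 10) would face the two-method question and about 0.7 (0.05 to 3) the apparent exemption. Every share after the CR count is assumed. The CR count is by central review at one data cut, whereas retreatment uses investigator-determined CR, so the true pool may differ. No efficacy analysis, sample size, power or error rate changes.

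**What to change.** In Section 7.1.5.2.2, replace the female contraception item and its definition with a sentence such as: *A woman of childbearing potential must agree to use a birth control method from Section 5.7.2 until 120 days after her last dose.*

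For the pregnancy-test item in 7.1.5.2.2 and for note n in flow chart 6.2, define the tested group as all women who are neither surgically sterilized nor postmenopausal under items 1 and 2 of Section 5.7.2. Do not use the whole 5.7.2 exemption here: item 3 would drop testing for women who are merely not heterosexually active.

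If two methods are wanted in the second course, state that rule in 5.7.2.

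The cost is two reworded items and one phrase in a footnote. It needs no new visit or data field; at most a few women gain a pregnancy test at a visit already scheduled.

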7.1.5.3 Post-treatment Visits

7.1.5.3.1 Safety Follow-up Visit

The mandatory Safety Follow-Up Visit should be conducted approximately 30 days after the last dose of trial treatment or before the initiation of a new antineoplastic treatment, whichever comes first. All AEs that occur prior to the Safety Follow-Up Visit should be recorded. Subjects with an AE of Grade > 1 will be followed until the resolution of the AE to Grade 0-1 or until the beginning of a new antineoplastic therapy, whichever occurs first. SAEs that occur within 90 days of the end of treatment or before initiation of a new antineoplastic treatment should also be followed and recorded.

Subjects who are eligible for retreatment with pembrolizumab (as described in Section 7.1.5.2.2) may have up to two safety follow-up visits, one after the Treatment Period and one after the Second Course Phase.

7.1.5.4 Follow-up Visits

Subjects who discontinue trial treatment for a reason other than disease progression will move into the Follow-Up Phase and should be assessed every 12 weeks (\pm 7 days) to monitor disease status. Subjects should receive a full physical examination and ECOG status, vital

signs and labs should be repeated with each assessment. Every effort should be made to collect information regarding disease status until the start of new antineoplastic therapy, disease progression, death, end of the study, or if the subject begins retreatment with pembrolizumab as detailed in Section 7.1.5.2.2. Information regarding post-study antineoplastic treatment will be collected if new treatment is initiated.

For subjects who achieve CR determined by the investigator and are in the Follow-Up Phase, when they experience disease progression determined by investigator assessment are eligible to receive retreatment with pembrolizumab according to the criteria in Section 7.1.5.2.2 will move from the follow-up phase to the Second Course Phase. Details are provided in Section 6.2 – Trial Flow Chart for Retreatment.

[figure not shown]
CCI

7.1.5.4.2 Survival Follow-up

Once a subject experiences confirmed disease progression or starts a new antineoplastic therapy, the subject moves into the survival follow-up phase and should be contacted approximately every 12 weeks to assess for survival status until death, withdrawal of consent, or the end of the study, whichever occurs first.

CCI

7.1.5.4.3 Survival Status

To ensure current and complete survival data is available at the time of database locks, updated survival status may be requested during the course of the study by the Sponsor. For example, updated survival status may be requested prior to but not limited to an external Data

Monitoring Committee (eDMC) review, interim and/or final analysis. Upon Sponsor notification, all participants who do not/will not have a scheduled study visit or study contact during the sponsor defined time period will be contacted for their survival status (excluding participants that have previously recorded a death event in the collection tool).

7.2 Assessing and Recording Adverse Events

An adverse event is defined as any untoward medical occurrence in a patient or clinical investigation subject administered a pharmaceutical product and which does not necessarily have to have a causal relationship with this treatment. An adverse event can therefore be any unfavourable and unintended sign (including an abnormal laboratory finding, for example), symptom, or disease temporally associated with the use of a medicinal product or protocol-specified procedure, whether or not considered related to the medicinal product or protocol-specified procedure. Any worsening (i.e., any clinically significant adverse change in frequency and/or intensity) of a preexisting condition that is temporally associated with the use of the Sponsor's product, is also an adverse event.

Changes resulting from normal growth and development that do not vary significantly in frequency or severity from expected levels are not to be considered adverse events. Examples of this may include, but are not limited to, teething, typical crying in infants and children and onset of menses or menopause occurring at a physiologically appropriate time.

Sponsor's product includes any pharmaceutical product, biological product, device, diagnostic agent or protocol-specified procedure, whether investigational (including placebo or active comparator medication) or marketed, manufactured by, licensed by, provided by or distributed by the Sponsor for human use.

Adverse events may occur during clinical trials, or as prescribed in clinical practice, from overdose (whether accidental or intentional), from abuse and from withdrawal.

Progression of the cancer under study is not considered an adverse event.

All adverse events that occur after the consent form is signed but before randomization/treatment allocation must be reported by the investigator if they cause the subject to be excluded from the trial, or are the result of a protocol-specified intervention, including but not limited to washout or discontinuation of usual therapy, diet, placebo treatment or a procedure. From the time of randomization/treatment allocation through 30 days following cessation of treatment, all adverse events must be reported by the investigator. Such events will be recorded at each examination on the Adverse Event case report forms/worksheets. The reporting timeframe for adverse events meeting any serious criteria is described in section 7.2.3.1. The investigator will make every attempt to follow all subjects with non-serious adverse events for outcome.

Electronic reporting procedures can be found in the EDC data entry guidelines. Paper reporting procedures can be found in the Investigator Trial File Binder (or equivalent).

Adverse events will not be collected for subjects during the pre-screening period (for determination of archival tissue status) as long as that subject has not undergone any protocol-specified procedure or intervention. If the subject requires a blood draw, fresh tumor biopsy etc., the subject is first required to provide consent to the main study and AEs will be captured according to guidelines for standard AE reporting.

7.2.1 Definition of an Overdose for This Protocol and Reporting of Overdose to the Sponsor

For purposes of this trial, an overdose will be defined as any dose exceeding the prescribed dose for pembrolizumab of 1000mg or greater. No specific information is available on the treatment of overdose of pembrolizumab. In the event of overdose, pembrolizumab should be discontinued and the subject should be observed closely for signs of toxicity. Appropriate supportive treatment should be provided if clinically indicated.

If an adverse event(s) is associated with (“results from”) the overdose of Sponsor's product or vaccine, the adverse event(s) is reported as a serious adverse event, even if no other seriousness criteria are met.

If a dose of Sponsor's product or vaccine meeting the protocol definition of overdose is taken without any associated clinical symptoms or abnormal laboratory results, the overdose is reported as a non-serious Event of Clinical Interest (ECI), using the terminology “accidental or intentional overdose without adverse effect.”

All reports of overdose with and without an adverse event must be reported by the investigator within 24 hours to the Sponsor either by electronic media or paper. Electronic reporting procedures can be found in the EDC data entry guidelines. Paper reporting procedures can be found in the Investigator Trial File Binder (or equivalent).

7.2.2 Reporting of Pregnancy and Lactation to the Sponsor

Although pregnancy and lactation are not considered adverse events, it is the responsibility of investigators or their designees to report any pregnancy or lactation in a subject (spontaneously reported to them) that occurs during the trial.

Pregnancies and lactations that occur after the consent form is signed but before randomization/treatment allocation must be reported by the investigator if they cause the subject to be excluded from the trial, or are the result of a protocol-specified intervention, including but not limited to washout or discontinuation of usual therapy, diet, placebo treatment or a procedure. Pregnancies and lactations that occur from the time of randomization/treatment allocation through 120 days following cessation of Sponsor's product, or 30 days following cessation of treatment if the subject initiates new anticancer therapy, whichever is earlier, must be reported by the investigator. All reported pregnancies must be followed to the completion/termination of the pregnancy. Pregnancy outcomes of spontaneous abortion, missed abortion, benign hydatidiform mole, blighted ovum, fetal death, intrauterine death, miscarriage and stillbirth must be reported as serious events

(Important Medical Events). If the pregnancy continues to term, the outcome (health of infant) must also be reported.

Such events must be reported within 24 hours to the Sponsor either by electronic media or paper. Electronic reporting procedures can be found in the EDC data entry guidelines. Paper reporting procedures can be found in the Investigator Trial File Binder (or equivalent).

